6.4. Treatment compliance

The administration of all study treatments (including IPs) should be recorded in the appropriate section of the eCRF.

The study treatment provided for this study will be used only as directed in this Clinical Study Protocol (CSP). The investigational product will be administered at the study site on treatment visits and within visit windows as specified in the SoA.

If IP cannot be administered at a scheduled treatment visit, it can be postponed as necessary and administered as soon as possible (preferably within visit window). When IP dosing needs to be postponed, it is recommended that all scheduled treatment visit procedures (except for IP administration) are still performed within the visit window.

Re-scheduled IP dose can be then administered at an unscheduled visit. Physical exam and vital signs assessment are the minimum procedures to be performed at this visit. For WOCBP, the urine pregnancy test must be performed; IP will be administered only when the result of the test is negative. It may also include remaining visit procedures (not performed at the scheduled visit) and additional assessments as deemed necessary by the investigator.

If the visit procedures cannot be conducted within the window (e.g. the patient is unable to attend the study site), then the entire visit will be re-scheduled along with IP dosing.

If a dose is significantly delayed it is recommended to keep at least 2-4 weeks interval before the next dose. If a postponed dose overlaps with the next treatment visit window, the postponed dose will be skipped, and the next dose of IP given at the regularly scheduled visit. The visit schedule will be always calculated from randomisation visit date.

Any change from the dosing schedule, dose interruptions, dose discontinuations should be recorded in the eCRF.

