7.1.1. Procedures for discontinuation of study treatment

At any time, patients are free to discontinue IP without prejudice to further treatment. A patient that decides to discontinue IP should always be asked about the reason(s) and the presence of any AEs.

All patients who prematurely discontinue IP during DB period should return to the study site and complete the procedures described for premature IPD visit within 8 weeks after the last dose of IP. At that visit, although no longer on IP, patients should be encouraged to remain in the study to complete all subsequent study visits, procedures, and assessments. Data collection should continue according to the study protocol. Note that in this case, the IPD visit replaces the nearest regular visit while the following visits continues until V11 week 56.

If the patient does not agree to complete all subsequent visits and procedures, the patient should be encouraged to stay in the study, keep the ePRO device, and continue selected visits until Week 56.

If the patient does not agree to continue in-person study visits, telephone visits should be performed to ensure the collection of endpoints and safety information. Patients will be encouraged to keep the ePRO device and do assessments, participate in the telephone visits, and return the ePRO device at the end of the DB period (Week 56). If a patient is not willing

to complete ePRO procedures, device should be returned at the IPD visit and the telephone follow-up visit should be continued. A patient that agrees to a modified follow-up visit is not considered to have withdrawn consent or to have withdrawn from the study. The decision on the selected follow-up option needs to be documented in the patients' medical records.

If a patient is not willing to participate further in the study after the IPD visit, the ePRO will be returned at the IPD visit. No further follow up visit is required after the IPD visit.

If patient decides to discontinue IP during OLE, he/she needs to complete the IPD visit at 8 weeks after the last dose of IP, and no further follow-up visit is required.

The reason for premature discontinuation of IP should be recorded in the eCRF.

See the SoA for data to be collected at the time of treatment discontinuation and follow-up and for any further evaluations that need to be completed.

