Symptoms associated with nasal polyps	
 • Change from baseline in nasal symptom score(s) as captured in the NP Symptom Diary (NPSD)
Patient-reported general health status	
 • Change from baseline in Short Form 36-item Health survey, Version 2 (SF-36v2),

	Physical Component Score (PCS), Mental Component Score (MCS) and domains
To characterize the Pharmacokinetics (PK) and immunogenicity of benralizumab	
 • PK: Serum trough concentrations • Immunogenicity: Anti-drug antibodies
Safety objective:	Endpoint/variable
To assess the safety and tolerability of benralizumab as compared to placebo in patients with Chronic Rhinosinusitis with Nasal Polyps	
Safety and tolerability will be evaluated in terms of adverse events (AE)s, Vital signs, Clinical laboratory, and electrocardiogram (ECG)
 
 • Assessments related to AEs cover 
 - Occurrence/Frequency - Relationship to investigational product (IP) as assessed by investigator - Intensity - Seriousness - Death - AEs leading to discontinuation of IP • Vital signs parameters include systolic and diastolic blood pressure, and pulse. Assessments cover 
 - Observed value - Absolute change from baseline values over time • Laboratory variables • ECG
Exploratory objectives	Endpoint/variable
To assess the effect of benralizumab on asthma control	
 • Asthma Control Questionnaire (ACQ-6) • Annual asthma exacerbation rate (AAER)
To assess the effect of benralizumab on patient recognition of improvement	
 • Patient Global Impression of Severity (PGI-S) • Patient Global Impression of Change (PGI-C)
To assess the effect of benralizumab on exploratory biomarkers of inflammation	Exploratory biomarker parameters:

and nasal polyps disease and investigate biomarkers for predicting response to benralizumab	
 • Serum and plasma for protein biomarkers • Whole blood for transcriptomic profiling • Nasal secretions for protein biomarkers
To assess the effect of benralizumab on CCI [REDACTED] as a biomarker of inflammation and nasal polyposis disease CCI [REDACTED]	
 • CCI [REDACTED]

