[a] For subjects enrolled from CSP v1.0 and v2.0 with efficacy endpoints (SNOT-22, UPSIT, SF-36) collected after Week 56, Week 56 is considered as Week Y in this table.

For visit-based safety summaries during the OLE period: There were 7 subjects who entered the OLE period after being followed up without IP dosing per CSP v1.0 or 2.0. Safety data collected from those subjects during the OLE period are grouped into each timepoint based on the relative duration to the first OLE dose. Specifically, Week 60 is the 2nd scheduled visit (~4 weeks) after the first OLE dose, and Week 64 is the 3rd scheduled visit (~8 weeks) after the first OLE dose, etc.

For local laboratory assessments (including vital signs, ECG), the nominal visit number reported by study sites in web-based data capture (WBDC) will be used in the visit-based summary. Similarly, nominal visit number recorded for scheduled PK assessments in the WBDC will be used for trough concentrations. Unscheduled PK assessments (where nominal visit number is not available) need to be 7-9 weeks (i.e. ± 7 days of Visit X) after the previous IP dosing at Visit X-1 in order to be considered as trough concentration at Visit X.

For overall analyses not based on any particular study visit (e.g. shift tables or event-based analysis), no analysis window will be applied; all data will be listed and/or analysed during analysis periods specified in Section 3.1.1, including any repeat or unscheduled assessments, unless otherwise specified.

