If there is strong evidence for a differential treatment effect for NPS and/or NBS across subgroups, additional analyses based on the NPS and/or NBS responder analysis may be conducted. Additional terms for the subgroup main effect and treatment \times subgroup interaction will be included in the logistic regression model defined in Section 4.2.5.4.

Subgroup analyses based on PK will also be performed for the change from baseline at Week 56 for co-primary and key secondary endpoints. All patients with at least one post-baseline PK sample collected will be included in this analysis. Patients on Benra will have their median PK concentration calculated based on all observed trough concentrations at steady state during the 56-week analysis period. Values collected after treatment discontinuation or without IP dosing at the previous visit will not be used to derive the median. Patients on Benra will then be grouped to PK quartiles based on their median concentration values and compared against the overall placebo group. A similar ANCOVA model, as described in Section 4.2.5.1 and Section 4.2.6.1 to Section 4.2.6.3, will be used with treatment group (i.e. Benra vs placebo) replaced by a 5-category PK variable (4 PK quartiles for benralizumab and 1 for placebo). Estimates of the treatment effects will be reported based on contrasts between each Benra quartile and placebo.

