4.2.8.1 Analysis of pharmacokinetic variables

Benralizumab serum concentrations will be summarised by using descriptive statistics during the DB period using the PK analysis set, and during the OLE period using the OLE analysis set. In addition, geometric mean, coefficient of variation (CV), lower (Q1), and upper (Q3) quartiles will also be reported.

Serum concentrations, that are below the LLOQ (<LLOQ) or if there are missing values, will be handled as follows:

- All values <LLOQ will be set to LLOQ/2. Missing values will be set to “NA”.
- At a time point where mean is <LLOQ, Not Applicable (N/A) will be written in the field for SD, CV%, and 95% CI. The maximum value will be reported from individual data. If median is <LLOQ then shall be reported as <LLOQ, otherwise reported from individual data. The minimum value will be reported as <LLOQ.
- If all values are <LLOQ at a time point, no descriptive statistics will be calculated for that time point. Not Applicable (N/A) will be written in the field for SD, CV%, and 95% CI, and <LLOQ will be written in fields for the mean, geometric mean, minimum, median and maximum.

The LLOQ of Benralizumab in serum will be 3.86 ng/mL.

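### Scheduled PK samples count as troughs by visit number alone, so off-drug, skipped-dose and late-dose samples enter the descriptive trough and PK-by-ADA summaries

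*SAP*

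**What the plan says.** The endpoint for the secondary PK objective is "PK: Serum trough concentrations" (SAP 1.2).

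SAP 3.1.2 has two rules for what counts as a trough:

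- Scheduled samples: "nominal visit number recorded for scheduled PK assessments in the WBDC will be used for trough concentrations".
- Unscheduled samples: they "need to be 7-9 weeks (i.e. ± 7 days of Visit X) after the previous IP dosing at Visit X-1".

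SAP 4.2.5.3 has a third rule, for the median concentration that defines the PK quartiles: "Values collected after treatment discontinuation or without IP dosing at the previous visit will not be used to derive the median".

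The summaries that report the PK endpoint (SAP 4.2.8.1) are descriptive and are made "during the DB period using the PK analysis set, and during the OLE period using the OLE analysis set". They contain no sample-level exclusion, and "All values <LLOQ will be set to LLOQ/2". SAP 8.7 summarises the same concentrations by ADA status for the double-blind, open-label and on-study periods, also without an exclusion for PK values. For ADA results, 8.7 does discard samples taken after dosing on a dosing day.

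On conduct, Protocol 7.1.1 says of patients who stop IP in the double-blind period that "patients should be encouraged to remain in the study to complete all subsequent study visits, procedures, and assessments". Protocol 6.4 recommends, when a dose is postponed, that "all scheduled treatment visit procedures (except for IP administration) are still performed within the visit window". It counts all visits from randomisation and skips a postponed dose that runs into the next visit window. Protocol 8.5.1 assays every double-blind PK sample from the benralizumab arm.

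**The concern.** A trough is defined by its relation to the preceding dose. The SAP accepts this for unscheduled samples and for the PK-quartile median, but not for the scheduled samples that supply most of the data for the endpoint. The protocol provides three routes by which a scheduled sample is not a trough: the patient has stopped IP and still attends, the dose just before the PK visit was skipped, or that dose was given late.

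At stake is the meaning of the reported troughs. A by-visit geometric mean and CV would mix 8-week values with values from other points on the concentration curve. PK by ADA status could be distorted as well if missed or late doses, or discontinuation, differ between ADA groups. The documents give no evidence either way on that.

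**Working it through.** **Inputs.** Doses at Weeks 0, 4, 8, 16, 24, 32, 40 and 48, then 56, 60, 64, 72, 80, 88, 96 and 104 in the extension (Protocol 4.1). Post-baseline PK samples at Weeks 16, 24, 40 and 56 (Protocol Table 2) and Weeks 80 and 112 (Table 3). Visit windows are ±3 days at Weeks 4 and 8 and ±7 days from Week 16 on. LLOQ 3.86 ng/mL (SAP 4.2.8.1).

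**1. The plan's own interval.** Every post-baseline PK visit falls 8 weeks after the preceding scheduled dose visit: 16−8, 24−16, 40−32, 56−48, 80−72, 112−104. Eight weeks ±7 days gives 7-9 weeks, which reproduces the rule for unscheduled samples.

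**2. What compliant visits allow.** The dosing visit has a window too.

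- Week 16: 56 ± (3+7) days = 46-66 days, or 6.6-9.4 weeks.
- Later PK visits: 56 ± (7+7) days = 42-70 days, or 6-10 weeks.

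**3. One skipped dose (double-blind period).**

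| Dose skipped | Next PK visit | Last dose received | Weeks since dose |
|---|---|---|---|
| Week 4 | 16 | 8 | 8 |
| Week 8 | 16 | 4 | 12 |
| Week 16 | 24 | 8 | 16 |
| Week 24 | 40 | 32 | 8 |
| Week 32 | 40 | 24 | 16 |
| Week 40 | 56 | 48 | 8 |
| Week 48 | 56 | 40 | 16 |

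Only the dose immediately before a PK visit matters. In the extension, skipping Week 72 or Week 104 likewise gives 16 weeks.

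**4. Late dose.** Protocol 6.4 recommends at least 2-4 weeks between a significantly delayed dose and the next one. The following pre-dose sample may then be only 2-4 weeks after dosing.

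**5. Discontinuation with continued visits.** Last dose at Week 8: 16, 32 and 48 weeks since dose at Weeks 24, 40 and 56. The extreme is a single dose at Week 0 sampled at Week 56, which is 56 weeks.

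**6. Size (illustration).** The current text gives no half-life. Assume mono-exponential decline with half-life h = 16.8-22.4 days. Concentration relative to the 8-week value, t weeks after dosing, is 2^(−7(t−8)/h).

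| Weeks since dose | h = 16.8 | h = 22.4 |
|---|---|---|
| 2 | 5.66 | 3.67 |
| 4 | 3.17 | 2.38 |
| 16 | 0.099 | 0.177 |
| 32 | 0.001 | 0.0055 |

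If a share f of samples sits at ratio r and the rest at 1, the geometric mean is multiplied by r^f.

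- Samples at 16 weeks: 0.177^0.05 = 0.917 and 0.099^0.10 = 0.794, a fall of 8-21% for f = 5-10%.
- Near-complete washout, r = 0.01: 0.01^0.05 = 0.794 and 0.01^0.10 = 0.631, a fall of 21-37%.
- Samples at 2-4 weeks: 2.38^0.05 = 1.04 and 5.66^0.10 = 1.19, a rise of 4-19%.

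The contributions have opposite signs, so the net shift depends on shares that the documents do not give. Both kinds of sample widen the spread.

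**The case against.** The strongest reply is that the effect is small and partly covered already. The summaries are descriptive, and the PK-quartile analysis has its own exclusion. Population PK is reported separately (Protocol 9.4.1.2). Mean, median and quartiles are given beside the geometric mean, and the median would move little with 5-10% of atypical samples. Sites are asked to make every effort to avoid missed doses, and patients off IP may choose telephone follow-up, which yields no blood sample. In the extension, patients who stop have one visit at 8 weeks after the last dose and no more (Protocol 7.1.1). All of this stands, and it limits the point to a definitional gap in secondary summaries.

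A second reply is that the PK analysis set (SAP 2.1.4) filters out affected samples, since it refers to factors such as protocol deviations and SAP 2.2 lists IP deviations. This stands only in part. The set might remove some patients by judgement, but it selects patients rather than samples and states no reproducible rule. Stopping IP with continued follow-up and postponing a dose are both permitted by the protocol. The open-label summary in 4.2.8.1 uses the OLE analysis set, which has no PK filter.

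A reader might also infer that the reported troughs will be biased down by a large amount. Setting every affected sample to LLOQ/2 = 1.93 ng/mL, with an assumed trough of 250 ng/mL, gives falls of 22% at a 5% share (0.00772^0.05 = 0.784) and 52% at 15% (0.00772^0.15 = 0.482). The documents do not support that as the expected size. On the same assumed trough and the half-lives above, a patient last dosed at Week 40 would be at about 25-44 ng/mL at Week 56, well above the LLOQ. Falling below 3.86 ng/mL takes log2(250/3.86) = 6.0 half-lives beyond week 8, or roughly 22-27 weeks after the last dose. Late doses also push the other way.

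**Conclusion.** The point holds as a gap in the definition of trough. SAP 3.1.2 admits scheduled samples whatever the time since dose, and 4.2.8.1 and 8.7 do not carry over the exclusion that the SAP itself uses in 4.2.5.3. The summaries for the secondary PK objective and for PK by ADA status can therefore contain values that are not troughs, with inflated spread and a net shift of unknown sign.

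The 8-21% fall is illustrative. It rests on an assumed half-life of about 17-22 days, mono-exponential decline, and an assumed 5-10% of samples taken 16 weeks after dosing. Larger falls need near-complete washout.

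Three stronger inferences are not supported. The documents give no rate of discontinuation, skipping or postponement, so it cannot be said that many samples are affected. Not every skipped dose matters: skipping Week 4, 24 or 40 leaves the next PK sample at 8 weeks. Efficacy conclusions are not touched: the co-primary and key secondary tests do not use these summaries, and the PK-quartile analysis already excludes off-treatment and undosed values.

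**What to change.** In SAP 3.1.2, 4.2.8.1 and 8.7, for the double-blind, open-label and on-study periods:

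1. Apply the 4.2.5.3 exclusion of values after treatment discontinuation or without IP dosing at the previous visit.
2. Count a scheduled sample as a trough only if it was taken before the dose (where one is given at that visit) and 6-10 weeks after the last IP dose. This is the range that two ±7-day windows allow. Applying the 7-9 week limit for unscheduled samples would discard some samples from fully compliant visits.
3. List the excluded samples with time since the last dose.

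The cost is SAP wording, one derivation and slightly fewer samples per visit. Protocol 8.5 already requires the date and time of each injection and sample, so no change to dosing, visits or data collection is needed.

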3.1.3 The definition of baseline

In general, the last valid value on or prior to the date of randomisation will serve as the baseline measurement for efficacy endpoints while the last valid value prior to first dose of study treatment will serve as the baseline measurement for safety endpoints. If there is no value prior to randomisation (or the first dose of study treatment, depending on the endpoint), then the baseline value will not be imputed and will be set to missing. No safety data known to be collected post first dose will be used in determining the baseline value, unless otherwise specified.

For the NPSD (which includes the NBS and DSS), the baseline is the mean of daily responses collected from Day -13 to Day 1. The mean is calculated as the sum of all non-missing daily scores if at least 8 days (>50%) over these 14 sequential days have available data, divided by the number of non-missing daily scores. Otherwise, the baseline is set to missing.

Baseline value for the OLE will be set to the last recorded value prior to starting the first dose of benralizumab in the OLE.

Summaries of demographics, safety, immunogenicity, etc. will be provided for the DB period and may be repeated for the OLE period using the OLE baseline values among all patients in the OLE analysis set including patients who were previously on benralizumab.

3.1.4 Definition of prior/concomitant medications

- For the DB period, a medication for CRSwNP/asthma will be classified as a maintenance medication at baseline if it started prior to or on the date of randomisation and is continued after randomisation.
- For the DB period, a medication will be regarded as prior if it was stopped on or before the date of randomisation (medication stop date \leq date of randomisation).
- For the DB period, a medication will be regarded as concomitant if the start date is after the date of randomisation, or if it started on or prior to the date of randomisation and was ongoing after the date of randomisation. Medications with start date on or after the end of the analysis period (as defined in Section 3.1.1) will not be considered as concomitant.
- Maintenance/prior/concomitant during the OLE period will be defined similarly as above where the first dose in OLE will be compared instead of randomisation date.

3.1.5 Derivation for response variables

Response variables will be derived for selected efficacy endpoints as mentioned in the sections below. For the response variables, patients will be classified as responders or non-responders based on the specified criteria under each endpoint. Patients with missing or non-evaluable observation at the timepoint of interest will be counted as non-responders in the

analysis. Patients who have had surgery or SCS use for CRSwNP by the timepoint of interest will be considered as non-responders unless otherwise specified.

3.2 Demographics and baseline characteristics

Following demographics and key subject baseline variables will be provided. Baseline definition is specified in Section 3.1.3.

- Age
- Gender
- Country
- Region
- Race
- Ethnicity
- Weight
- Height
- BMI
- Nicotine use
- Nicotine consumption

Important baseline variables for CRSwNP and respiratory disease characteristics will be provided including but not limited to:

- number and percentage of subjects with prior surgery for CRSwNP
- number of prior surgery for CRSwNP
- number and percentage of subjects with prior SCS use for CRSwNP
- number of SCS use for CRSwNP in the past 12 months
- JESREC (<11 vs \geq 11)
- any aspirin exacerbated respiratory disease (AERD)/nonsteroidal anti-inflammatory drug exacerbated respiratory disease (NERD)
- CCI
- baseline blood eosinophil count
- atopic disease CCI
- anosmia (based on UPSIT \leq 18)

Important baseline variables for asthma disease characteristics will be provided including but not limited to:

- number of prior asthma exacerbations in the past 12 months
- number of prior SCS use for asthma in the past 12 months
- number of emergency room visit due to asthma in the past 12 months
- number of hospitalization due to asthma in the past 12 months
- baseline ACQ-6 score
- number and percentage of subjects using any ICS component (including maintenance and as needed use) at baseline
- number and percentage of subjects on maintenance ICS at baseline
- total daily ICS dose for asthma maintenance medications at baseline

3.3 Primary efficacy variables

According to the SoA Table 2 and Table 3 in the CSP, co-primary efficacy assessments will be collected during the DB period only. Therefore, derivation of co-primary endpoints applies to the DB period and will be reported at the primary DBL.

